Exclusion Criteria:

- Under 18 years old
- Does not speak English
- Unable to consent to involvement in the research study

- Is pregnant
- Has a bleeding disorder/diagnosis
- Currently taking anticoagulant medications and not stopped for procedure
- Documented low platelets (<100,000)
- Had a biopsy taken immediately prior to the endobronchial ultrasound

Sample Size Determination: A power analysis was conducted using a small to medium effect size (0.3), power of 0.8, and level of significance 0.05. It was determined that 44 patients would be needed in each group, for a total sample size of 88 patients. To allow for the possibility of removing participants from the final analysis due to missing data, we plan to enroll 120 patients (60 in each group).

- **Data Collection**

Before the study begins, information about the study will be provided to the providers and endoscopy team members, including information about the study purpose, inclusion/exclusion criteria, and procedures.

When a patient who meets the inclusion/exclusion criteria arrives for an appointment, a nurse from the study team will describe the study, answer any questions the patient has, and if the patient wants to enroll in the study, the study team nurse will review the information consent form. After the patient provides written informed consent, the nurse will remove the next envelope out of a box of prefilled and sealed opaque envelopes. The envelope will provide the Subject ID number to be used on all study-related documentation and the study Arm that the patient has been randomized to, either:

1. Cold saline group
2. Standard care group

These envelopes will be filled using a computerized simple random number generator (1:1 randomization) prior to the start of the study.

In addition to the group assignment, the envelope will include a data collection form. Data will be recorded directly on this form during the patient's visit. The form will collect the following information:

- Whether patient was assigned to the cold saline group or the standard care group
- Patient demographics including age, gender, current anticoagulant medications, current cancer diagnoses
- Temperature of cold saline (cold saline group only)
- Time cold saline placed (cold saline group only)
- Volume of cold saline used for irrigation
- Time each biopsy was obtained
- Number of biopsies
- Gauge of needle used to perform biopsy
- Type of suction used (i.e. slow-pull or 5mL, 10mL)

- Number of slides prepared

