- Number of slides that were successfully read
- Number of slides unable to be read due to blood on slide
- Whether another biopsy was attempted
- Whether the procedure was stopped without successful slide reading
- Whether patient needed epinephrine post-biopsy to stop bleeding
- Name of MD performing biopsy
- Start and end time of procedure

After the procedure, the RN will complete the data collection form and place the signed informed consent form and data collection form in the locked resource nurse's office in an area designated for study materials.

On the data collection forms, RNs are instructed to call a member of the study team immediately if there are any safety concerns related to the cold saline. If the study team receives a call about a safety concern, recruitment and enrollment of new participants will stop until the study team meets and reviews the incident with the pulmonologist involved and determines it is safe to continue. The study team includes nurses with clinical experience and expertise in endobronchial biopsy procedures. They will consult with the medical team if any adverse events arise. Any adverse events and serious adverse events will be reported to the IRB in compliance with IRB safety policies.

- **Intervention or experimental aspect of the study**

In patients randomized to Arm 1, the clinician will scan the cold saline using the infrared temperature scanner and confirm saline is between 33-39 degrees Fahrenheit. Then after identifying the lymph node or lesion to be biopsied on ultrasound, using the endobronchial ultrasound scope, two 60mL syringes of cold saline will be inserted, through the biopsy channel of the endobronchial ultrasound scope, directly onto the bronchial wall where the biopsies are to be performed. The saline will then be sucked out of the airway using the endobronchial ultrasound scope. The FNA needle or biopsy forceps will then be passed down the biopsy channel of the endobronchial ultrasound scope, and the biopsy will be obtained. Cold saline irrigation is part of the normal procedure and may cause coughing. The study may benefit these patients if the preventive cold saline irrigation prevents bleeding.

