Patients randomized to Arm 2 will receive standard care that includes no irrigation with cold saline prior to the biopsy. After identifying the lymph node or lesion to be biopsied on ultrasound, the FNA needle or biopsy forceps will then be passed down the biopsy channel of the endobronchial ultrasound scope, and the biopsy will be obtained.

In both Arm 1 and Arm 2, TriHealth pulmonologists will conduct the endobronchial ultrasound and biopsy according to standard clinical practice. Patients will receive the same care procedure and biopsy that they would receive if they were not enrolled in the study. The only research procedure is that patients in Arm 1 will receive irrigation of the biopsy site with cold saline before the biopsy is performed. The rest of the procedure will follow standard clinical practice.

Data recorded on paper data collection forms will be entered into a password protected database. Only study team members will have access to the database. No personal information will be entered into the electronic database. Data will undergo range checks when entered in the database, and quality control procedures will be performed to ensure accuracy of the data in the electronic database.

- **Statistical Analysis**

Statistical analyses will be performed using Intellectus Statistics statistical software. The following analyses will be performed to address each hypothesis:

- Hypothesis 1: Patients undergoing endobronchial ultrasound and biopsy who receive irrigation with cold saline prior to biopsy will experience a lower incidence of unreadable biopsy slides compared to patients undergoing endobronchial ultrasound and biopsy who do not receive irrigation with cold saline prior to biopsy.

To compare the effects of the intervention, a Chi Square test will be used to compare frequency of unreadable biopsy slides among patients who received the cold saline irrigation compared to patients who did not receive the cold saline irrigation. A level of significance of $\alpha=0.05$ will be used.

- Hypothesis 2: Patients undergoing endobronchial ultrasound and biopsy who receive irrigation with cold saline prior to biopsy will experience a lower incidence of having to reperform biopsies in order to obtain readable slides compared to patients undergoing endobronchial ultrasound and biopsy who do not receive irrigation with cold saline prior to biopsy.

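### Hypothesis 1 does not define its unit of analysis; if slides are pooled, the ordinary chi-square ignores within-patient correlation and its type I error exceeds 5%

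*Combined protocol and SAP*

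**What the plan says.** **Hypothesis and test.** Hypothesis 1 is that irrigated patients "will experience a lower incidence of unreadable biopsy slides compared to patients undergoing endobronchial ultrasound and biopsy who do not receive irrigation". Under Statistical Analysis, "a Chi Square test will be used to compare frequency of unreadable biopsy slides among patients who received the cold saline irrigation", against those who did not receive it, at a significance level of 0.05. The section does not say whether the table counts slides or patients, and it names no method for several slides from one patient.

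**Data.** The form described under Data Collection has "Number of slides prepared", the number read successfully, and "Number of slides unable to be read due to blood on slide". All are counts per patient. The outcomes for Hypotheses 2 to 4 have yes/no items on the same form: another biopsy attempted, procedure stopped without a reading, epinephrine needed. Hypothesis 1 has no such item.

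**Randomization and sample size.** Allocation is by patient, one envelope each. Under Sample Size Determination, "A power analysis was conducted using a small to medium effect size (0.3), power of 0.8, and level of significance 0.05", and "It was determined that 44 patients would be needed in each group, for a total sample size of 88 patients". Enrolment of 120 is planned to allow for missing data.

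**Repeat sampling.** The Background section says that blood contamination leads to further biopsies in the same patient.

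**Interim looks.** The end of Statistical Analysis plans looks at about one third and two thirds of enrolment, with data collection ending if outcomes differ significantly between groups.

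**The concern.** An ordinary chi-square assumes that the entries in its table are independent. Slides from one patient come from the same person in the same procedure, so a positive correlation between them is to be expected. If slides are the entries, the test credits the trial with more independent information than it has, and the standard error behind the p-value is too small.

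Repeat sampling adds to this. If bloody slides lead to more biopsies, patients who bleed may supply more slides and weigh more in the pooled table.

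At stake is a false positive finding on the first-listed hypothesis, the one closest to the study's stated purpose. If the same test is used at the interim looks, the trial could also stop early on it. That adds to the separate question of repeated testing.

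The numerator is also loose. The hypothesis speaks of unreadable slides in general, while the form isolates those lost to blood.

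**Working it through.** **1. The plan's own figure.** Inputs from Sample Size Determination: effect size 0.3, power 0.8, alpha 0.05. The plan does not name the effect index. Read as Cohen's w in a two-sided chi-square with 1 df:

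N = (1.960 + 0.842)² / 0.3² = 87.2, rounded up to 88, or 44 per group.

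The noncentral chi-square gives 80.4% power at N = 88. A one-sided test would give 69 in total. An effect size of 0.3 read as d or h would give 175 per group (two-sided). So the stated figure reproduces as 88 independent observations, and the plan counts them as patients.

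**2. Error rate if slides are pooled.** The documents do not give slides per patient (m) or the ICC, so both are assumed. With equal m:

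- design effect DE = 1 + (m − 1) × ICC
- true two-sided type I error = 2 × [1 − Φ(1.96 / √DE)]

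Worked example, m = 6 and ICC = 0.2: DE = 1 + 5 × 0.2 = 2.0; 1.96 / √2.0 = 1.386; error = 16.6%.

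| Slides per patient | ICC 0.05 | ICC 0.1 | ICC 0.2 | ICC 0.3 | ICC 0.5 |
|---|---|---|---|---|---|
| 3 | 6.2% | 7.4% | 9.8% | 12.1% | 16.6% |
| 6 | 8.0% | 11.0% | 16.6% | 21.5% | 29.5% |
| 10 | 10.4% | 15.5% | 24.1% | 30.8% | 40.3% |

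**3. Simulation check.** Settings, all assumed except the 44 patients per arm: beta-binomial data, 30% of slides unreadable, no treatment effect, 20,000 runs.

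- 3 slides per patient: the unadjusted test rejected in 7.3%, 12.1% and 16.7% of runs at ICC 0.1, 0.3 and 0.5.
- 8 slides per patient: 13.0%, 26.4% and 35.9%.
- A patient-clustered test, run at 3, 5 and 8 slides, stayed between 4.5% and 5.1%.

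**4. When bloody slides lead to more slides.** The same simulation, sampling until 3 slides are readable or 8 have been made, averaged 4.4 to 4.5 slides per patient. The formula in step 2, at the same mean number of slides, gives the comparison:

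| ICC | Mean slides | Formula, fixed m | Simulated, unadjusted | Simulated, patient-clustered |
|---|---|---|---|---|
| 0.1 | 4.37 | 9.0% | 11.6% | 5.5% |
| 0.3 | 4.50 | 17.1% | 21.9% | 5.7% |
| 0.5 | 4.54 | 23.9% | 29.6% | 5.7% |

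Under this assumed rule, outcome-dependent sampling makes the pooled test worse than its average slide count suggests.

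**5. Does the unit mismatch imply too few patients?** If w = 0.3 applied to slides, the patients needed would be 88 × DE / m. For m = 4 and ICC 0.3: 88 × 1.9 / 4 = 41.8, so 42. Since DE cannot exceed m when ICC is at most 1, the requirement never exceeds 88.

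**The case against.** **A patient-level table may have been intended.** The test sentence speaks of frequency among patients, and the sentences for Hypotheses 2 to 4 follow the same template with outcomes recorded once per patient. Randomization and sample size both count patients. A yes/no result per patient could be derived from the slide counts. On that reading there is no clustering and no inflation. This stands, and it means a reader should not conclude that the Hypothesis 1 p-value will certainly be too small. It does not clear the plan: no patient-level outcome is defined anywhere, and choosing the unit after seeing the data would itself threaten validity.

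**The size is assumed.** This also stands. Slides per patient, ICC and the unreadable rate appear nowhere in the documents. With few slides and a weak correlation the excess is small (6.2% at 3 slides and ICC 0.05).

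**Stronger inferences fail.** A reader might infer that the trial is too small because the sample size counts patients and the hypothesis counts slides. Step 5 of the working shows no shortfall. A reader might also infer that a reported confidence interval would be too narrow, but the plan specifies none for Hypothesis 1.

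**Conclusion.** The point holds as a specification gap with a conditional consequence. What is certain is that Hypothesis 1 names slides as the thing counted, holds its data only as slide counts, prescribes an ordinary chi-square, and defines neither a patient-level outcome nor a method for clustering. If slides are pooled, the type I error exceeds 5% whenever patients contribute more than one slide and slides within a patient are positively correlated. The illustrative range is about 6% to 40% over 3 to 10 slides and ICC 0.05 to 0.5, both assumed. If one yes/no result per patient is analyzed, clustering adds no inflation. The consequence is confined to the p-value and any interim stopping decision that uses it. The gap should be closed before analysis, including before the first interim look.

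**What to change.** Make the patient the unit for Hypothesis 1 and name one primary analysis in Statistical Analysis. The numerator is "Number of slides unable to be read due to blood on slide" and the denominator is "Number of slides prepared". Choose one of these in advance:

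- **Per-patient proportion.** Compute each patient's proportion of prepared slides lost to blood and compare arms with every patient weighted equally, for example by a Mann-Whitney test. Equal weighting stops patients with many slides from dominating.
- **One yes/no outcome per patient.** Define it explicitly (for example, any slide lost to blood) and keep the chi-square. An 'any slide' outcome becomes more likely as more slides are made, so report slide counts by arm beside it.

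State how a patient with no slides prepared is handled. Use the same definition at the interim looks. Any slide-level analysis should be supportive, with patient-clustered robust standard errors, for example a logistic GEE. A first-pass analysis (one result per patient from the first biopsy) is optional and would need a few extra boxes on the form.

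The cost is a few sentences in the plan and a little more analysis work. The primary analysis needs no new data and no extra patients. The p-value will usually be larger than the pooled one.

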- Hypothesis 4: Patients undergoing endobronchial ultrasound and biopsy who receive irrigation with cold saline prior to biopsy will experience a lower incidence of requiring epinephrine to control bleeding after the biopsy compared to patients undergoing

endobronchial ultrasound and biopsy who do not receive irrigation with cold saline prior to biopsy.

Background

Endobronchial ultrasounds are used to investigate lymph nodes and/or lesions within or next to the patient's lungs that are visible on ultrasound. The procedure can be used in the diagnosis or staging of cancer. Fine needle biopsies can be obtained through the endobronchial ultrasound scope, and the tissue obtained is immediately placed on cytology slides and promptly taken outside the room to the mobile cytology cart to be stained. The pathologist will then read the prepared slides in real time, offering feedback as to what cells are seen. However, red blood cells often contaminate the sample, due to bleeding from the biopsy site, and thus potentially cover up and block the obtained specimen. This causes more biopsies to be taken and prolongs the procedure and anesthesia time. During normal bronchoscopies, cold saline is used, and has been studied, to decrease bleeding in the airways. This study evaluates the use of cold saline irrigation BEFORE biopsies are taken to potentially decrease the risk of bleeding. Irrigating with cold saline preventatively BEFORE biopsies are taken is not common practice. Additionally,, there has been no research conducted investigating the use of cold saline prior to bronchial biopsies being taken to decrease bleeding. This study seeks to fill this gap in the literature.

Research Plan

- **Study Design**

This study will use a randomized, non-blinded, controlled design with two arms:

- Arm 1: Patient will receive irrigation with 120mL of cold saline 33-39 degrees Fahrenheit), delivered in two 60mL syringes, prior to biopsy
- Arm 2: Patient will receive standard care which involves biopsy without prior irrigation with cold saline.

- **Setting for the study**

The study will take place on Bethesda North Hospital's Endoscopy Department. This unit provides care to approximately 2-12 patients undergoing an endobronchial ultrasound and biopsy per week.

- **Participants**

The study will enroll 120 patients who meet the following inclusion/exclusion criteria:

Inclusion Criteria:

- Undergoing an endobronchial ultrasound and biopsy at Bethesda North Hospital

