To compare the effects of the intervention, a Chi Square test will be used to compare frequency of having to reperform biopsies among patients who received the cold saline irrigation compared to patients who did not receive the cold saline irrigation. A level of significance of $\alpha=0.05$ will be used.

- Hypothesis 3: Patients undergoing endobronchial ultrasound and biopsy who receive irrigation with cold saline prior to biopsy will experience a lower incidence of stopping the procedure without biopsy results compared to patients undergoing endobronchial ultrasound and biopsy who do not receive irrigation with cold saline prior to biopsy.

To compare the effects of the intervention, a Chi Square test will be used to compare frequency of stopping the procedure without biopsy results among patients who received the cold saline irrigation compared to patients who did not receive the cold saline irrigation. A level of significance of $\alpha=0.05$ will be used.

- Hypothesis 4: Patients undergoing endobronchial ultrasound and biopsy who receive irrigation with cold saline prior to biopsy will experience a lower incidence of requiring epinephrine to control bleeding after the biopsy compared to patients undergoing endobronchial ultrasound and biopsy who do not receive irrigation with cold saline prior to biopsy.

To compare the effects of the intervention, a Chi Square test will be used to compare frequency of epinephrine administration to control bleeding after the biopsy among patients who received the cold saline irrigation compared to patients who did not receive the cold saline irrigation. A level of significance of $\alpha=0.05$ will be used.

Interim data analysis will occur (1) once approximately 1/3 of the participants have been enrolled in each group and (2) once approximately 2/3 of the participants have been enrolled in each group. If interim calculations at time (1) or time (2) note a significant difference in outcomes between groups, data collection will be completed at that time and final analysis will be completed.

Ethical Considerations

- **Informed consent**

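### The H1–H4 tests group patients by whether they received cold saline, and nothing in the plan says they are analysed as randomised

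*Combined protocol and SAP*

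**What the plan says.** The Study Design section states: "This study will use a randomized, non-blinded, controlled design with two arms". The assigned arm comes from a sealed envelope, and the data collection form records it.

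The Statistical Analysis section does not define its groups by that assignment. The H1 paragraph compares unreadable slides "among patients who received the cold saline irrigation compared to patients who did not receive the cold saline irrigation". The H2 paragraph compares the "frequency of having to reperform biopsies among patients who received the cold saline irrigation compared to patients who did not receive the cold saline irrigation". H3 and H4 use the same grouping phrase. The two interim looks are described only as comparing outcomes between groups.

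No section names an intention-to-treat, as-randomised, as-treated or per-protocol set, or says how to class a patient whose treatment differs from the envelope. On missing data, the only text is in Sample Size Determination, where enrolment is raised from 88 to 120: "To allow for the possibility of removing participants from the final analysis due to missing data". There is no rule for when a patient is removed, and no sensitivity analysis.

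**The concern.** Randomisation balances the envelope arms. It does not balance groups formed by what happened in the procedure room. An Arm 1 patient may go without irrigation because the saline is out of its temperature range or because irrigation is not feasible. An Arm 2 patient may be irrigated before a later biopsy pass. If such departures relate to bleeding risk, grouping by receipt builds that risk into the comparison. Bleeding is what the intervention targets, and it plausibly affects all four outcomes. The staff who give or withhold irrigation also know the arm.

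The form would let receipt and assignment diverge in the data. Saline temperature and time are limited to the cold saline group, but saline volume is not. An analyst following the text could therefore group patients by volume.

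Unexplained removal for missing data is a second, smaller route to the same problem. A procedure stopped before a slide is read may have no usable H1 result, so missingness could depend on outcome.

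**Working it through.** **The plan's own figure.** Inputs from Sample Size Determination: effect size 0.3, power 0.80, significance level 0.05. The type of effect size and the sidedness are not stated. Taking Cohen's w and a two-sided 1-df chi-square test:

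N = (1.960 + 0.842)² / 0.3² = 87.2, rounded up to 88, or 44 per group.

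This reproduces the plan. The sample size is not affected by this point.

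**Bias from grouping by receipt.** The following are assumptions, not figures from the document: no true effect, 50% overall risk in each arm, a share q of Arm 1 not irrigated with risk r, and full adherence in Arm 2. The 60 per arm is the plan's.

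- Risk among those who received: (0.5 − q·r) / (1 − q), in 60(1 − q) patients.
- Risk among those who did not: (30 + 60·q·r) / (60 + 60q), in 60(1 + q) patients.

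For q = 10%, 6 patients move, giving groups of 54 and 66:

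- r = 70%: received (0.5 − 0.07)/0.9 = 47.8%; not received (30 + 4.2)/66 = 51.8%. False benefit 4.0 points.
- r = 90%: received (0.5 − 0.09)/0.9 = 45.6%; not received (30 + 5.4)/66 = 53.6%. False benefit 8.1 points.

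Type I error is Φ((d − 1.96·se₀)/se₁) + Φ((−d − 1.96·se₀)/se₁), where d is the false difference, se₀ the pooled standard error and se₁ the unpooled one. For r = 70%, d = 0.040 and se₀ and se₁ are both about 0.092, which gives 7.2%.

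| Arm 1 not irrigated | False benefit, r = 70% to 90% | Type I error |
|---|---|---|
| 0% | 0 points | 5.0% |
| 5% | 2 to 4 points | 5.5% to 7.2% |
| 10% | 4 to 8 points | 7.2% to 14.2% |
| 20% | 8 to 17 points | 14.4% to 43.1% |

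If the non-irrigated patients carry average risk (r = 50%), the bias is zero at every q.

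**Opposite direction.** Assume 40% risk in both arms, so 24 events in 60, and that 6 Arm 2 patients with the event are counted as having received saline. The rates become (24 + 6)/66 = 45.5% and (24 − 6)/54 = 33.3%. This bias runs against saline, and the difference is not significant (z = 1.35, p = 0.18).

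**Missing outcomes, extreme case.** Take true risk 30/60 in both arms and 4 removed from each, all with the event in one arm and all without it in the other. The complete-case rates are 26/56 = 46.4% and 30/56 = 53.6%.

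**Cost of analysing as assigned.** Assume true rates of 65% and 35% (w = 0.3 at a 50% average), 60 per arm, and non-irrigated Arm 1 patients at 65%. Power by assigned arm is 0.918, 0.887, 0.850, 0.806 and 0.756 when 0%, 5%, 10%, 15% and 20% of Arm 1 is not irrigated.

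**The case against.** The best defence is that the verb is loose shorthand for the assigned arm. The arm definitions use it the same way: "Arm 2: Patient will receive standard care which involves biopsy without prior irrigation with cold saline". The envelope options are themselves called groups, and the interim text compares groups. Irrigation is a single step, so departures may be rare. This makes the intent uncertain, but it does not settle it. The protocol speaks of assignment and randomisation elsewhere and does not do so where the tests are defined.

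Some stronger readings are tempting, but the documents do not support them.

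- A reader might infer that the randomised comparison is lost. That needs risk-related departures from assignment, and the document gives no rate for them. The comparison is unprotected, which is a weaker statement.
- A reader might infer that Arm 2 patients given saline to treat bleeding would count as treated, because of "During normal bronchoscopies, cold saline is used, and has been studied, to decrease bleeding in the airways" and "Cold saline irrigation is part of the normal procedure and may cause coughing". But every hypothesis specifies irrigation before biopsy, and the second sentence sits in the description of Arm 1. Saline after a biopsy is a weak route; irrigation before a further pass is the arguable one.
- A reader might infer that the plan permits removal of 32 patients (120 − 88). That number is an enrolment buffer. Removal is mentioned only as a possibility, with no ceiling.
- A reader might infer that the envelope should be opened later. The envelope supplies the subject number and data form, and the saline temperature check comes before the target is identified, so a later opening would conflict with the described procedure. Eligibility is also to be met before consent.

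**Conclusion.** The point holds in limited form. As written, all four tests group patients by saline received, and no analysis population is defined. The rule that would preserve the randomised comparison is therefore absent from the place where it is needed.

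The size is conditional. With 10% of Arm 1 not irrigated and a 70–90% risk in those patients against 50% overall, the false benefit is 4–8 points and the type I error about 7–14%. With full adherence, or departures unrelated to risk, there is no bias. The adherence and risk inputs are assumptions. Because a significant interim difference ends data collection, the rule should be settled before the first interim look.

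**What to change.** In each of the H1–H4 paragraphs, replace the received / did not receive wording with randomised to Arm 1 / randomised to Arm 2. Then add the following:

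- Every randomised patient is analysed in the envelope arm, at both interim looks and at the final analysis.
- A patient is left out only of an outcome that is actually missing, and missing outcomes are reported by arm.
- The as-treated comparison is kept as a sensitivity analysis only.
- For H1, a sensitivity analysis counts procedures stopped without a readable slide as failures. It should not replace the main endpoint, because the form records unreadable slides as due to blood and a procedure may stop for other reasons.

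The cost is a few sentences and no new data, since the form already records the assigned arm. The downside is slight dilution of the estimate by non-adherence. On the assumed 65% and 35% rates, power stays above 80% with up to about 15% of Arm 1 not irrigated.

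### Two interim looks that force a stop on an undefined significant result, with 0.05 the only level given, put the two-sided error at about 11% per outcome instead of 5%

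*Combined protocol and SAP*

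**What the plan says.** All references are to the combined protocol and SAP.

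- **Research Plan, Statistical Analysis.** Each of Hypotheses 1 to 4 (unreadable slides, repeat biopsy, procedure stopped without results, epinephrine use) gets its own chi-square test. For each: "A level of significance of $\alpha=0.05$ will be used".
- **Same section, closing paragraph.** The first interim analysis comes "once approximately 1/3 of the participants have been enrolled in each group" and the second at about 2/3. If either should "note a significant difference in outcomes between groups, data collection will be completed at that time and final analysis will be completed". Stopping is required, not advisory.
- **Participants, Sample Size Determination.** "A power analysis was conducted using a small to medium effect size (0.3), power of 0.8, and level of significance 0.05". The result: "It was determined that 44 patients would be needed in each group, for a total sample size of 88 patients". To allow for missing data, "we plan to enroll 120 patients (60 in each group".

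The documents give no interim threshold other than 0.05, no group-sequential boundary or alpha spending, no primary outcome, no multiplicity rule, and no statement of which outcome, or how many, must be significant for the trial to stop.

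**The concern.** A test repeated on accumulating data at an unchanged 0.05 has three chances to cross the line, so its error rate is no longer 5%. Here crossing the line also ends the trial. An ineffective irrigation would then produce significant results, and early closure, more often than the stated level implies.

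Two further consequences follow from the open trigger and the small first look. A stop caused by one outcome ends the tests of the other three at whatever size the trial has reached. And a difference that is significant with about 20 patients per arm must be very large, so estimates from a trial stopped there will tend to be exaggerated.

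**Working it through.** **Inputs from the documents.** Effect size 0.3, power 0.8, alpha 0.05, 44 per group required, 60 per group planned, 1:1 allocation, looks at about 1/3 and 2/3. The looks therefore fall at about 20, 40 and 60 per arm (40, 80 and 120 patients). **Assumed, because the documents are silent:** event rates, correlations between outcomes, and no continuity correction.

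**1. The plan's own figure.** Taking 0.3 as Cohen's w for a chi-square test with 1 df:

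N = (1.960 + 0.842)² / 0.3² = 7.85 / 0.09 = 87.2, rounded up to 88, or 44 per group.

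This reproduces. Power by the non-central chi-square is 80.4% at 88 and 90.8% at 120. Reading 0.3 as Cohen's d or h gives 175 per group, so w with the uncorrected two-sided test is what was used.

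**2. One outcome, three looks.** Under the null the Z statistics at information fractions 1/3, 2/3 and 1 are standard normal, with correlation √(t_j/t_k) for t_j < t_k. By simulation:

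P(|Z| > 1.96 at any look) = 10.7%.

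An exact binomial calculation with the uncorrected chi-square at 20/40/60 per arm gives:

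| Event rate | Three looks |
|---|---|
| 10–50% | 10.6–11.1% |
| 5% | 7.6% |
| 2% | 2.2% |

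With a Yates correction the figure is about 3–6% for rates of 10–50%. In the direction of benefit only, the three-look rate is 5.4% against a nominal 2.5%. It is 4.7–4.8% if the trial stops on any outcome and each outcome is then tested once.

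**3. At least one false positive among four outcomes, any one of which can stop the trial.** For a single look under independence the rate is 1 − 0.95⁴ = 18.5%. The other figures are simulated.

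| Assumed correlation | Single final look | Three looks |
|---|---|---|
| 0 | 18.5% | 36.5% |
| 0.5 | 15.5% | 30.9% |
| 0.7 | 13.0% | 26.2% |
| 0.8 | about 11% | 23.1% |

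The looks roughly double the rate in every row. The null chance of stopping early on some outcome is 29% at correlation 0 and 25% at 0.5.

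**4. What a first-look stop leaves for Hypothesis 1.** At 40 patients and w = 0.3 the non-centrality is 40 × 0.09 = 3.6. Power ≈ Φ(√3.6 − 1.96) = Φ(−0.063) = 47.5%, about 48%.

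**5. Smallest significant gap at 20 per arm, rates near 50%.** For event counts a and c, χ² = 40 × [20(a − c)]² / [20 × 20 × (a + c)(40 − a − c)].
- 13/20 v 7/20 (30 points): 40 × 14,400 / (400 × 20 × 20) = 3.60, below 3.84.
- 14/20 v 7/20 (35 points): 40 × 19,600 / (400 × 21 × 19) = 4.91, significant.

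The smallest attainable significant gap is 35 points.

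**6. Effect of a boundary on one outcome.** O'Brien-Fleming with constant 2.004 sets |Z| limits of 2.004√3 = 3.47, 2.004√1.5 = 2.45 and 2.00 (nominal p about 0.0005, 0.014 and 0.045). Simulated type I error is 5.0%. Haybittle-Peto (3.29, 3.29, 1.96) gives 5.1%.

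**The case against.** The strongest reply is that the plan promises 5% for each hypothesis and never an overall 5%. A reader might infer that the stopping rule lifts an overall 5% to 26–37%. The documents do not support that. Four unadjusted tests at one final look already give about 11–18%, and that part is a separate multiplicity matter. The overall range also rests on correlations and event rates that the documents do not give. The outcomes look clinically linked, so high correlation is plausible, and at 0.8 the figure is 23%.

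A reader might also infer that an ineffective irrigation would be declared a success 11% or 26–37% of the time. Those rates are two-sided and count significant harm. The hypotheses are directional, and a false claim of benefit on a given outcome is about 5%.

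Third, the text refers to a difference in outcomes; it does not say that any one outcome suffices. If only Hypothesis 1 could stop the trial, the overall rate would be about 16–23%. If all four had to be significant, it would be about 12–19%, with 5–6% per outcome.

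Finally, rare outcomes or a continuity correction lower the per-outcome rate. The protocol mentions no correction, and its sample size reproduces without one.

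All of this stands as a limit on the overall figure. It does not rescue the rule. The per-outcome 10.7% needs no correlation assumption, and it remains for Hypothesis 1 even if that outcome alone is the trigger. The all-four reading would largely avoid it, but nothing in the text states that reading.

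**Conclusion.** The concern holds and must be fixed. With 0.05 applied at each look, as the text implies by giving no other level, an outcome tested three times has a two-sided type I error of about 10.7%. This assumes an uncorrected chi-square and event rates of roughly 10–50%. It breaks the plan's own 5% per hypothesis.

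The trigger is undefined. On the any-of-four reading, the chance of at least one false positive is about 23–37% for assumed correlations of 0.8 to 0, against about 11–18% without interim looks. That range is illustrative and should not be set against an overall 5% that the plan does not claim.

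A first-look stop on another outcome would leave Hypothesis 1 with about 48% power at w = 0.3.

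**What to change.** Replace the interim paragraph with wording that does the following.

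1. Designates one primary outcome. The documents name none, so this is a new decision for the sponsor. Hypothesis 1 is the natural choice: it is listed first and matches the stated purpose.
2. Lets only that outcome trigger efficacy stopping, with O'Brien-Fleming two-sided nominal p of about 0.0005, 0.014 and 0.045 at 40, 80 and 120 patients. Alternatives are Haybittle-Peto (p < 0.001 at both interims, 0.05 at the end) or no efficacy stopping at all.
3. Leaves Hypotheses 2 to 4 untested at the interims, and labels them secondary or adjusts them for multiplicity, for example by Holm. The boundary alone does not deal with them: with each still tested at 0.05, the overall error stays at about 11–18%.
4. States whether the chi-square test carries a continuity correction.

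**Cost.** One paragraph of text. O'Brien-Fleming power at w = 0.3 is 90.3% against 90.8% at 120 patients, and 79.7% against 80.4% at 88, a loss of under one percentage point. The downside is that a stop at 1/3 becomes unlikely: at w = 0.3 its chance is about 1 − Φ(3.47 − √3.6) = 1 − Φ(1.57), or about 6%.
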